Patients with metastatic urothelial cancer will receive Atezolizumab intravenously at 1200mg every three weeks or Pembrolizumab at a flat dose of 200mg every three weeks (Physician's discretion). Patients will continue to receive infusions every two or three weeks for up to three years or until disease progression or until a dose limiting toxicity is reached.

Patients randomized to the radiotherapy arm will receive radiation every other day. A dose of 10 Gy x3 days will be administered.

Primary Objectives: The primary aim is to estimate the difference in best overall response (BOR; time frame: 96 weeks) rates using RECIST version 1.1, in patients with metastatic renal cell/urothelial carcinoma when treated with immunotherapy alone and immunotherapy plus radiotherapy (to a single metastatic site).

[figure not shown]
Secondary Objectives: The secondary aims are: 1) to estimate the median progression free survival and the median overall survival for patients treated with immunotherapy and immunotherapy plus radiotherapy, and 2) to assess the toxicity (per CTCAE version 4.0) of patients treated with immunotherapy and immunotherapy plus radiotherapy.

**Exploratory
(Correlatives)
Objectives:**

Exploratory analyses will include: 1) examination of an association between clinical responses and anti-tumor immune responses (cellular and humoral responses) and 2) comparison of T cell subsets within tumors and in the peripheral blood at baseline versus at the time of response evaluation.

Endpoints: The primary endpoint will be BOR (time frame: 96 weeks) rates as evaluated using RECIST version 1.1. Other end points include progression free-survival and overall survival.

SCHEMA
Please see study calendar (section 14.0) for additional screening procedures and treatment windows

- *Renal cell cancer patients – Nivolumab (flat dose of 240mg) q2 weeks up to 3 years. Immune labs to be drawn prior to infusion on Days 1, 29 and 57.
- *Urothelial cancer patients – Nivolumab (flat dose of 240mg) q2 weeks up to 3 years or Atezolizumab (1200mg) q3 weeks up to 3 years or Pembrolizumab (flat dose of 200mg) every 3 weeks up to 3 years. Immune labs to be drawn prior to infusion on Days 1, 43 and 64.
- Radiation (10 Gy x3 fractions) will be delivered on days 1, 3 and 5.
- ‡ MRI brain for patients in the RENAL Cancer cohort only.

Table of Contents

DOCUMENT HISTORY : 6

SUMMARY OF CHANGES : AMENDMENT 1 DATED 12.15.2016 6

PROTOCOL SUMMARY 7

SCHEMA..... 9

1.0 Study Objective 13

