12.3 Off Study Criteria

- Intercurrent illness that prevents further administration of treatment
- Unacceptable toxicity
- Patient decides to withdraw from the study
- General or specific changes in the patient's condition render the patient unacceptable for further treatment in the judgment of the investigator

Authorized Physicians must notify the data manager and Principle Investigator when a patient is taken off study.

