Radiation Therapy^e - ARM B		X	X	X						
Endocrine Panels ^c	X				X	X				
Genomic Bloods/T-cell collection		X ^f				X ^f	X ^f			
Tumor biopsies	X ^g							X ^g		

- a. Before each infusion.
- b. SOC labs (COMP, CBC w/diff.)
- c. TSH, T3, T4
- d. Scans day 63 ± 7.
- e. Radiation is given to one, randomly selected lesion 30Gy in 3 fractions of 10 Gy each (ARM B only)
- f. to be collected PRIOR to infusion on days 1,43 and 64.
- g. Optional biopsy done at Day 63(±7 days).
- h. infusions will have a ± 3 day window.
- i. prior scans will be valid until the screening period of 28 days,
- j. infusions will be ±24hrs from Day 1 of radiation. k. Patients will come off-study if they have disease progression. Patients will be followed for 30 days from the day they come off-study.

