17.3.2 Safety Assessments

All patients who receive at least one dose of Immunotherapy will be considered evaluable for safety parameters. Additionally, any occurrence of a SAE from time of consent up to and including follow-up visits will be reported. Refer to safety reporting section 6.2

Safety will be evaluated for all treated patients using the NCI CTCAE version 4.03 (<http://ctep.cancer.gov>). Safety assessments will be based on medical review of AE reports and the results of vital sign measurements, physical examinations and clinical laboratory tests.

1.12.1.1 17.4 Criteria for Evaluation

1.12.1.1.1 17.4.1 Safety Evaluation

This protocol will be monitored by the WCM Data Safety Monitoring Committee which oversees the safety of all WCM investigator initiated clinical trials. The trial will be monitored for all adverse events, laboratory abnormalities, and serious adverse events at least once every 12 months. In addition, serious adverse events are monitored for all studies on a monthly basis.

1.12.1.1.2 17.4.2 Efficacy Evaluation

For the purposes of this study, patients should be re-evaluated for response every 9 weeks, in year 1, every 12 weeks in years 2 and 3. Confirmatory scans may also be obtained 4 weeks following initial documentation of objective response or progressive disease.

Response and progression will be evaluated in this study using the international criteria proposed by the Response Evaluation Criteria in Solid Tumors (RECIST) guideline (version 1.1). Patients will be followed for scans every 9 weeks for the first year or until disease progression and every 12 weeks after the first year or until disease progression.

Measurable and non-measurable lesions:

- Measurable disease: Measurable lesions are defined as those that can be accurately measured in at least one dimension (longest diameter to be recorded) as ≥ 20 mm (≥ 2 cm) by chest x-ray or as ≥ 10 mm (≥ 1 cm) with CT scan, MRI, or calipers by clinical exam. All tumor measurements must be recorded in millimeters (or decimal fractions of centimeters).
- Malignant lymph nodes: pathologically enlarged and measurable lymph node must be ≥ 15 mm (≥ 1.5 cm) in short axis when assessed by CT scan (CT scan slice thickness recommended to be no greater than 5 mm [0.5 cm]). At baseline and in follow-up, only the short axis will be measured and followed.

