Note: If tumor markers are initially above the upper normal limit, they must normalize for a patient to be considered in complete clinical response.

Non-CR/Non-PD: Persistence of one or more non-target lesion(s) and/or maintenance of tumor marker level above the normal limits.

Progressive Disease (PD): Appearance of one or more new lesions and/or unequivocal progression of existing non-target lesions. Unequivocal progression should not normally trump target lesion status. It must be representative of overall disease status change, not a single lesion increase.

Although a clear progression of “non-target” lesions only is exceptional, the opinion of the treating physician should prevail in such circumstances, and the progression status should be confirmed at a later time by the review panel (or Principal Investigator).

1.13.1.3 18.3 Evaluation of Overall Response Criteria

The best overall response is the best response recorded from the start of the treatment until disease progression/recurrence (taking as reference for progressive disease the smallest measurements recorded since the treatment started). The patient's best response assignment will depend on the achievement of both measurement and confirmation criteria. Revised Response Evaluation Criteria in Solid Tumors (RECIST) Version 1.1

1.14 19.0 Response According to Revised Response Evaluation Criteria in Solid Tumors Version 1.1

Target Lesions	Non-Target Lesions	New Lesions	Overall Response	Best Overall Response when confirmation is Required
CR	CR	No	CR	≥ 4 weeks confirmation
CR	Non-CR/Non-PD	No	PR	≥ 4 weeks confirmation
CR	Not Evaluated	No	PR	
PR	Non-CR/Non-PD/Not Evaluated	No	PR	
SD	Non-CR/Non-PD/Not Evaluated	No	SD	Documented at least once ≥ 4 weeks confirmation from baseline
PD	Any	Yes or No	PD	No prior SD, PR or CR.
Any	PD	Yes or No	PD	
Any	Any	Yes	PD	

CR = Complete response; PD = Progressive Disease; PR=Partial response; SD =Stable disease.

1.15 20.0 Response Endpoints

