This study will be conducted in accordance with the guidelines in the 2001 NCI approved data Safety and Monitoring plan for the WCM Cancer Institute and with the WCM approved data Safety and Monitoring plan for the WCM Cancer Institute. Monitoring will occur on a semi-annual basis from the date the first patient is enrolled. Reports to the Data Safety and Monitoring Committee will include the following information: accruals, targets, responses, adverse events and evidence of reporting to appropriate review committees. The WCM Data and Safety Monitoring Board (DSMB) will review the IRB approved protocol, the data and safety monitoring plan and any stopping guidelines during protocol initiation. The WCM DSMB may also convene as needed if stopping criteria are met or other safety issues arise that the Principal Investigator and/or IRB would like the WCM DSMB to address. The study team will meet on a monthly basis to review AE data and a copy of the report will be sent to the study statistician. As per the DSMB review dated 30AUG2019, a final study report once available will be submitted to the DSMB for their final review.

1.22.1.2 27.2 Stopping Rules

Treatment will be held if patients experience hematological or non-hematological toxicities while on therapy. Patients will be monitored until resolution of the adverse event to grade 0 or baseline. Based on PI's discretion, patients will resume or be withdrawn from study. In addition, the study will also follow the dose modification

tables, [9.6](#) and [10.4](#) for nivolumab and atezolizumab for holding therapy or to permanently withdraw patients from study. Adverse events will be recorded based on CTCAE v4.03.

1.23 28.0 Data Management

Data will be entered into the REDCap database and maintained at WCM by trained Radiation Oncology data manager [name].

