1. Distribution of changes in T cells from baseline to response evaluation.
2. Association between abscopal responses and T cell changes from baseline. Changes from baseline in immune responses will be summarized over the time course of the study and post treatment using descriptive statistics and graphical displays. The patterns of changes in immune parameters will be examined using exploratory statistical approaches to assess the relationship of changes in individual parameters to clinical outcomes. Mixed effects regression models and general estimating equations will be used to compare the patterns of change in immune response over time in the two treatment groups.

Changes from pretreatment to follow up levels of immunologic parameters and other parameters described above in irradiated tumors (and non-irradiated tumors) will be compared between the two treatment groups using descriptive statistics and graphical displays.

All patients will be followed for progression-free survival and overall survival. Kaplan-Meier curves for progression-free survival and overall survival will be provided to summarize the results.

1.24.1.2 29.2 Interim Analyses

A futility analysis will be conducted after 50% of the total 18-week RECIST responses (estimated median time to response ~14 weeks) for final analysis have occurred (i.e., N/2 of N). No accrual suspension is required to conduct the futility analysis. If at this point the relative risk of no response in the immunotherapy arm over the immunotherapy plus radiation arm is 1.0 or less, the study will be stopped for futility.

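### The protocol contradicts itself on whether patients who stop immunotherapy without progression stay in tumour assessment, which leaves 96-week BOR and PFS open to early truncation

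*Combined protocol and SAP*

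**What the plan says.** **Endpoints.** The Protocol Summary states: "The primary endpoint will be BOR (time frame: 96 weeks) rates as evaluated using RECIST version 1.1". Section 18.3 sets the recording period: "The best overall response is the best response recorded from the start of the treatment until disease progression/recurrence". It adds: "The patient's best response assignment will depend on the achievement of both measurement and confirmation criteria". Section 17.4.2 sets the imaging: "Patients will be followed for scans every 9 weeks for the first year or until disease progression", then every 12 weeks, also until progression. Section 29.1 says: "All patients will be followed for progression-free survival and overall survival". None of these ends when drug stops.

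**Operational rules.** Section 12.3, headed as off-study criteria, begins with "Intercurrent illness that prevents further administration of treatment" and goes on to unacceptable toxicity, patient withdrawal and investigator judgment. Section 17.2 gives the same items as reasons for discontinuing study drug. Section 27.2 offers two outcomes after a toxicity hold, at the investigator's discretion: resume, or be withdrawn from the study. It then applies the drug tables "for nivolumab and atezolizumab for holding therapy or to permanently withdraw patients from study". The tables themselves (9.3 and 10.3) only withhold or permanently discontinue drug. Footnote k of both calendars (sections 15.0 and 16.0) says: "Patients will be followed for 30 days from the day they come off-study".

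**The concern.** The operational sections describe no state in which a patient is off drug but still being scanned. A patient with stable disease, or with a first partial response, who stops for toxicity can be recorded as off study and leave 30 days later. With scans 9 or 12 weeks apart, those 30 days often contain none.

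Two things are at stake. For the primary endpoint, a response that appears or is confirmed after exit is not seen, and no analysis can recover a scan that was not done. For PFS, the patient is censored at a time set by toxicity, which may be related to prognosis and may differ by arm.

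**Working it through.** **1. The passages side by side.**

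| Question | 12.3, 27.2, footnote k | 17.4.2, 18.3, 29.1 |
|---|---|---|
| Status after a toxicity stop without progression | Off study | Still under assessment |
| Last tumour assessment | Within 30 days of exit | Progression |
| Basis for BOR | Scans up to exit | Best response until progression, 96-week frame |
| Basis for PFS | Censored at exit | All patients followed |

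No sentence says which set prevails. Section 29 has no rule for patients who leave without progression, either for counting them in BOR or for censoring them in PFS.

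**2. What the 30 days would remove.** The schedule gives about nine scans by Week 96: Weeks 9, 18, 27, 36, 45, 57, 69, 81 and 93. Section 3.6.1 gives a median onset of immune-mediated pneumonitis in renal cell carcinoma of 3.82 months, about Week 17. Exit at Week 17 plus 30/7 weeks ends follow-up at about Week 21.3. That captures 2 of 9 scans and leaves 96 − 21.3 = 74.7 weeks unobserved. Exit at Week 12 ends follow-up at Week 16.3, after one scan. For comparison, section 29.2 puts median time to response at about 14 weeks, and the nivolumab trial in section 3.4 reports confirmed responses starting as late as 13.0 months, about Week 56.

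**3. The plan's own power figure.** Inputs from section 29.0 and 29.1: 56 per arm, 20% against 40%, one-sided alpha 0.20, Fisher's exact test. Full enumeration gives 90.2%, matching the stated 90%.

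**4. Effect on BOR under stated assumptions.** Let *w* be the fraction who leave before a response is seen and confirmed, and *s* the share of their responses lost. Then the observed rate is *p* × (1 − *w* × *s*). For example, with *w* = 10% and *s* = 1, the rates are 0.20 × 0.90 = 18% and 0.40 × 0.90 = 36%.

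| *w*, Arm A / Arm B | *s* | Observed rates | Difference | Fisher power |
|---|---|---|---|---|
| none | – | 20.0% / 40.0% | 20.0 points | 90.2% |
| 4% / 4% | 0.5 | 19.6% / 39.2% | 19.6 | 89.7% |
| 4% / 4% | 1 | 19.2% / 38.4% | 19.2 | 89.2% |
| 10% / 10% | 0.5 | 19.0% / 38.0% | 19.0 | 88.9% |
| 10% / 10% | 1 | 18.0% / 36.0% | 18.0 | 87.5% |
| 10% / 25% | 0.5 | 19.0% / 35.0% | 16.0 | 81.6% |
| 10% / 25% | 1 | 18.0% / 30.0% | 12.0 | 68.2% |

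**5. Which rows have support.** No overall stop rate is given. A partial count is possible from the renal cell data in section 3.6, using grades for which the protocol stops nivolumab permanently: pneumonitis Grade 3–4, 5 patients; hepatitis Grade 3, 5; adrenal insufficiency Grade 3, 3; nephritis Grade 4–5, 2. That is 15/406 = 3.7% if no patient is counted twice. For atezolizumab (section 4.5), pneumonitis and hepatitis of Grade 3 or worse give (2 + 6)/523 = 1.5%. Both counts omit infusion reactions, other events, intercurrent illness and investigator judgment, so 4% is a reference point and 10% a cautious assumption. The 10% / 25% rows are illustrative only.

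**The case against.** The strongest reply is that the protocol does not actually order truncation. Sections 12.3 and 27.2 contain no follow-up length. In footnote k the 30-day sentence directly follows one about coming off study at progression, and in section 17.2 the 30 days sit inside the patient-withdrawal item only. Section 17.2 is also headed as drug discontinuation, so the protocol has that category. Section 21.7 gives patients whose adverse events stop treatment further follow-up as appropriate. All of this stands. Applying 30 days to toxicity exits is an inference, though a natural one: the footnote's sentence is not restricted to progression, and 12.3 and 27.2 provide other routes off study.

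A reader might infer three stronger things.

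- **That follow-up is definitely cut short.** The text supports a contradiction, not a settled rule.
- **That an early partial response is bound to be lost.** Take a response at Week 9 with drug stopped at Week 11. Follow-up would run to about Week 15, and the 4-week confirmatory scan allowed by 17.4.2 would fall at Week 13, inside that window. The response is lost only if that optional scan is not done.
- **That power falls to 82% or 68%.** This needs 25% stopping in Arm B against 10% in Arm A. No passage supports that imbalance: section 2.3.6 describes radiotherapy as largely free of systemic effects, and section 20.0 calls this dose standard palliation.

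Timing also softens the effect on BOR. Median onsets in section 3.6 are 3.7 months for hepatitis, 3.82 for pneumonitis, 4.8 for diarrhoea or colitis, 5.4 for nephritis and 5.8 for adrenal insufficiency. All are later than the 3.0-month median onset of confirmed response in section 3.4, so many stops would follow the response.

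**Conclusion.** The contradiction is real, and it bears on whether primary and secondary endpoint data are collected. Its likely cost to BOR is modest: with equal early exit of 4% to 10% in both arms, power drops by about 0.5 to 2.7 points, from 90.2% to between 89.7% and 87.5%. That range rests on assumed exit fractions and on half or all of the affected responses being lost.

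The more direct harm is to PFS, where each toxicity exit becomes an early and possibly informative censoring. It is not quantified here, because the documents give neither a stop rate nor a PFS assumption. The point should be fixed. It does not by itself undermine the primary comparison.

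**What to change.** Separate leaving treatment from leaving the study, and reconcile 12.3, 17.2, 27.2 and footnote k with 17.4.2, 18.3 and 29.1:

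- In 12.3, present toxicity, illness and investigator judgment as reasons to leave treatment.
- In 27.2, replace both references to withdrawing patients from the study with wording on discontinuing study drug. The section also cites the tables as 9.6 and 10.4, while they stand at 9.3 and 10.3.
- In footnote k of both calendars, limit the 30-day sentence so that it does not end tumour assessment in patients who have not progressed. Without this change, the edits above would still conflict with the calendars.
- State that patients who stop drug without progression stay on the existing 9- and 12-week scans until progression, death, withdrawal of consent or loss to follow-up: to Week 96 for BOR, and to the end of planned follow-up for PFS.
- In section 29, say how patients who still leave early are counted for BOR and censored for PFS.

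The rules on when drug is held or stopped are not at issue and stay as they are. The cost is one wording amendment, plus continued imaging, on a schedule 17.4.2 already contains, for the minority who stop early.

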Full Title:	Phase II randomized trial of PD-1/PDL-1 axis blockade versus PD-1/PDL-1 axis blockade plus radiotherapy in metastatic genitourinary (renal/urothelial) malignancies
Short Title:	Immunotherapy Plus Radiotherapy in Genitourinary Malignancies
Clinical Phase:	Phase II
Principal Investigator:	[name], M.D. .
Sample Size:	N = 112
Accrual Ceiling:	129
Study Population:	Eligible patients have metastatic renal cell carcinoma/urothelial carcinoma with at least 2 measurable sites of disease.
Accrual Period:	We expect to accrue up to 112 patients over three years and at an accrual rate of approximately 40 patients per year.
Study Design:	Eligible patients have metastatic renal cell carcinoma/urothelial carcinoma with at least 2 measurable sites of disease. All eligible patients will be randomly assigned to immunotherapy (Nivolumab/Atezolizumab/Pembrolizumab) versus immunotherapy (Nivolumab/Atezolizumab/ Pembrolizumab) plus radiotherapy, 10 Gy x3 (conformally or by IMRT/IGRT to maximally spare normal tissue), to one of their measurable lesions. For patients assigned to the immunotherapy plus radiotherapy arm, immunotherapy treatment starts with the first radiotherapy fraction. Nivolumab will be given every 2 weeks for patients with metastatic renal cell cancer and Atezolizumab (flat dose 1200mg) or Pembrolizumab (flat dose 200mg) will be given every 3 weeks for patients with metastatic urothelial cancer. Patients will be re-imaged at 9 week (year 1) or 12 week (years 2-3) intervals and evaluated for response (defined as an objective response of measurable metastatic sites outside the radiation field). This response will be evaluated with CT scans in non-irradiated measurable metastatic sites per RECIST version 1.1. Patients will continue to receive their respective immunotherapies for up to three years or until disease progression or until a dose limiting toxicity is reached.

Study Duration: *Participants will have approximately up to 25-35/yr visits and a follow-up for up to 3 years.*

**Study Agent/
Intervention:**

Patients with metastatic renal cell carcinoma will receive Nivolumab intravenously at a flat dose of 240mg every two weeks. Infusions will be given over 60 minutes (not bolus or IV push). Patients will continue to receive infusions every two weeks for up to three years or until disease progression or until a dose limiting toxicity is reached.

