11.0 Radiation Therapy Guidelines

11.1 Planning

After a lesion to be treated with radiotherapy is identified, the site is imaged at the time of CT simulation. Contrast Media may be used during the CT simulation, as deemed necessary by the treating physician. CT scan thickness should be <0.5 cm through the tumor bed region. These images will be used in treatment planning in accordance with the dose specific constraints per the Task Group 101 of the American Association of Physicists in Medicine.

The clinical tumor volume (CTV) is defined as the lesion of interest with the expected motion changes. The planning target volume (PTV) is the CTV + a 0.5-1 cm margin for setup error.

Respiratory gating may be used during the CT simulation to delineate an internal target volume (ITV) for chest and abdominal lesions that are subject to motion during the respiratory cycle. In this setting, a 0.5-1cm margin for setup error will be added to the ITV to establish the PTV.

Treatment Planning: 3D-Conformal or Intensity Modulated Radiation Therapy (IMRT) treatment planning is allowed. This includes “field-in-field” beams as well as the use of dynamic multi-leaf collimator (MLC) derived using inverse planning or electronic compensator techniques. Field arrangements and technique should be chosen that satisfy the PTV_{eval} and normal tissue dose constraints (TG101) using Dose-Volume Histogram (DVH) analysis by carefully selecting the gantry and table angle combinations that do not enter or exit through other organs of the body, the dose can be confined to the traditional treatment volumes. Non-coplanar beam arrangements are encouraged, but not required. Dose calculations with tissue inhomogeneity correction must be used. Beams entering lesions that will be monitored for abscopal responses will be avoided.

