The system provides audit trails that track creation and modification of records that include user ID and timestamp. Once entered, the data is subjected to validation procedures that are executed either immediately or upon saving the eCRF page or during the batch validation process. Validation failures that are identified before the page is saved can be corrected immediately. Validation failures during saving of the eCRF page and during batch validation processes will generate a discrepancy. Depending on the database account privileges, the data managers may be able to correct a discrepancy or if not, route it to the project data manager at WCM who can take appropriate action to correct the problem. Data clarification forms can also be printed out when necessary to be sent to the project data manager. Once the discrepancy is closed, by marking “resolved” or “irresolvable”, the data is marked clean and an audit trail is generated by the system.

All key end points will be source verified by a second person and errors will be corrected. Once the data is verified and all discrepancies are closed, the data can be locked/frozen. Locking and freezing can be done at different granular levels and will follow institutional SOPs and any specific requirements for the project.

Security measures that will be taken in order to protect patient data will include firewall technology and database level security which will be achieved by assigning roles and privileges to different levels of users and by requiring that the users authenticate themselves using user ID and password. Additional security for data transfer between remote clients and servers will be achieved by using digital certificates/SSL. All data will be backed-up to tape periodically according to the Institutional SOPs. All data will be stored for at least 5 years following the termination of this study.

1.24 29.0 Statistical Considerations

112 patients will be randomly assigned in a 1:1 ratio to treatment with immunotherapy (Nivolumab or Atezolizumab) or to treatment with immunotherapy (Nivolumab or Atezolizumab) plus radiotherapy in this phase II trial. With 56 patients per group, if the expected response rate (PR or CR) is 20% with immunotherapy alone, we can detect a response rate of 40% for immunotherapy plus radiotherapy with a 1-sided alpha of 20% and a power of 90%.

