Forty patients per year will be randomized to the trial over ~ 3 years of accrual, assuming an accrual rate of approximately 20 patients per year for each cohort (see study calendar).

1.24.1.1 29.1 Statistical analysis

Both arms will run in parallel but will be analyzed separately. When the target accrual is met for a cohort, it will be closed to accrual even though other cohorts may still be accruing. Analyses will be done separately for each arm. Analyses will be similar for the two arms.

The primary objective of this study is the comparison of best overall response rates between each arm after start of treatment. Fisher's Exact test will be used to estimate 95% confidence intervals for the difference and to perform a one-sided test with an alpha level of 20%. Response rates for each arm will also be estimated at this level. With 56 patients treated under each modality, if the true responses are 20% and 40% in the immunotherapy alone and immunotherapy and radiation arms, respectively, we have a 90% probability of detecting a difference between modalities. Secondary objectives include time to disease progression and mortality. Median times for these events will be estimated with 95% confidence intervals. Graphical summaries will include Kaplan-Meier curves and log-rank tests which will be used to detect differences between treatments. Median survival and progression times will be estimated if sufficient events are observed. Cox proportional hazards regression will be used to account for baseline characteristics. Stratified exploratory analyses by type of cancer (renal cancer cell carcinoma or urothelial carcinoma) will also be performed.

Toxicities will be summarized per arm and prepared using Chi-square or Fisher's Exact tests, where appropriate.

Patient and disease characteristics will be summarized and compared at randomization between the two treatment arms using descriptive statistics and graphical displays. Although randomization will remove systematic biases we will test for differences in arms using Chi-square or Fisher's exact methods for categorical variables and t-tests or Kruskal-Wallis tests (with appropriate transformations of data if necessary for continuous variables). Differences in RECIST outcomes within each patient comparing non-irradiated and irradiated lesions will be summarized. Similar techniques will be used for exploratory analyses of the following:

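### The primary response comparison has no defined efficacy population and is worded around treated patients, which would favour radiotherapy if more patients are lost before Day 1 in Arm B than in Arm A

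*Combined protocol and SAP*

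**What the plan says.** Section 29.0 sizes the trial on allocation: "112 patients will be randomly assigned in a 1:1 ratio", which is 56 per arm. Section 29.1 then words the primary objective as the "comparison of best overall response rates between each arm after start of treatment" and repeats the power statement in different terms: "With 56 patients treated under each modality". Section 18.3 sets the same origin for the endpoint: "The best overall response is the best response recorded from the start of the treatment".

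The two arms reach that origin by different routes. For Arm B the Protocol Summary says "immunotherapy treatment starts with the first radiotherapy fraction"; section 6.2 allows 24 hours either side of Day 1. The first fraction depends on planning. Section 11.1 says "After a lesion to be treated with radiotherapy is identified, the site is imaged at the time of CT simulation", and a plan that respects normal-tissue dose limits must follow. Arm A has no such step.

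The only rule on who is evaluable is in section 17.3.2. It concerns safety and takes in any patient given one or more immunotherapy doses. There is no counterpart for response. The documents do not say how a randomised but untreated patient is counted or whether such a patient may be replaced. They give no limit on the time from randomisation to Day 1 and no time origin for PFS or OS.

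**The concern.** Followed literally, 29.1 and 18.3 leave a patient who is randomised and never starts with no place in the primary comparison. That would do little harm if such patients were equally common in both arms. Arm B, however, has an additional step before any treatment, immunotherapy included. If planning is done after randomisation, a patient who declines radiotherapy, has no acceptable plan or deteriorates in the interval may never reach Day 1. A comparable Arm A patient may already have had a first dose and would count as a non-responder.

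The documents describe no blinding, so the allocation is known when these losses occur. Leaving out more poor-prognosis patients from Arm B than from Arm A would raise its response rate with no treatment effect. What is at stake is the randomised comparison, in a design that already accepts a one-sided 20% false-positive rate.

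**Working it through.** **Inputs.** From 29.0 and 29.1: 56 patients per arm, response rates of 20% and 40%, one-sided alpha 0.20, power 90%, Fisher's exact test. The documents give no rate of loss before treatment, so a range is assumed.

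**1. The plan's own figure.** The usual formula for two proportions, with z = 0.8416 and 1.2816 and mean rate 0.30, is

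n = [0.8416 × √(2 × 0.30 × 0.70) + 1.2816 × √(0.20 × 0.80 + 0.40 × 0.60)]² / 0.20² = (0.5454 + 0.8105)² / 0.04 ≈ 46 per arm.

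With the continuity correction, (n/4) × [1 + √(1 + 4/(n × 0.20))]² rounds up to 56 per arm, which matches the plan. Exact enumeration of the one-sided Fisher test at 56 against 56 gives power 90.2%. At 20% against 20% the actual type I error is 14.5%, because the test is conservative. The stated power therefore reproduces, and the issue is who is counted.

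**2. Arm B losses replaced, so that 56 are treated in each arm.** Assume 20% response among all randomised patients in both arms, no loss in Arm A, and every lost patient a non-responder. With lost share d, the Arm B rate among treated patients is 0.20/(1 − d). Type I error is the sum of the binomial probabilities of all outcomes that the Fisher test rejects.

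| Arm B loss | Arm B rate | Fisher type I error |
|---|---|---|
| 0% | 20.0% | 14.5% |
| 5% | 0.20/0.95 = 21.1% | 18.0% |
| 7% | 0.20/0.93 = 21.5% | 19.7% |
| 10% | 0.20/0.90 = 22.2% | 22.4% |
| 15% | 0.20/0.85 = 23.5% | 27.9% |

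The nominal 20% is passed a little above 7% loss.

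**3. Losses not replaced.** Of 56 randomised per arm, 0.20 × 56 = 11.2 respond on average. If k non-responders are dropped, the rate is 11.2/(56 − k).

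| Lost from A, B | Rates A, B | Fisher type I error |
|---|---|---|
| 0, 2 | 20.0%, 20.7% | 15.6% |
| 0, 4 | 20.0%, 21.5% | 20.3% |
| 0, 6 | 20.0%, 22.4% | 20.2% |
| 0, 8 | 20.0%, 23.3% | 27.5% |
| 2, 4 | 20.7%, 21.5% | 15.4% |
| 3, 3 | 21.1%, 21.1% | 14.3% |
| 4, 4 | 21.5%, 21.5% | 14.3% |

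The steps are uneven because the test is discrete. The inflation comes from the difference in loss between arms; equal losses give none.

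**4. All randomised patients counted.** With untreated patients as non-responders, 56 against 56 keeps the type I error at 14.5%. Power is 90.2% if 40% is the Arm B rate among randomised patients. If 40% is instead the rate among treated patients and only Arm B loses patients, its rate is 0.40 × (1 − d):

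- 5% loss: 38%, power 86.1%
- 10% loss: 36%, power 80.8%
- 15% loss: 34%, power 74.4%

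If both arms lose the same share, power is 88.9%, 87.5% and 85.8%.

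**The case against.** The strongest reply is that exclusion is inferred. No sentence removes untreated patients from the response analysis. The reference to the start of treatment may fix only the time origin, and the 56 treated in 29.1 are the same 56 that 29.0 assigns, so the two words may be interchangeable. Section 29.1 also compares characteristics at randomisation and follows all patients for PFS and OS. This stands as a possible reading. But the text equally supports a treated-patient analysis, and two statisticians could follow it and analyse different patients.

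Several stronger readings are tempting but not supported:

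- **Only Arm B loses patients, because Arm A can be infused at once.** Arm A also has steps before the first dose: insurance cover for the drug (17.3.1), pregnancy testing where it applies, and Day 1 procedures. The documents do not say whether planning precedes or follows randomisation, and baseline evaluations may be at most 4 weeks old at the start of treatment in both arms (17.4.2), which limits the delay.
- **The accrual ceiling is there for replacement.** The ceiling of 129 exceeds 112 by 17, but no reason is given. It could equally cover patients registered soon after consent (22.1) who then fail screening. It does not bound the loss in Arm B.
- **PFS and OS carry immortal time.** No origin is stated for either. If population and clock both began at treatment start, no immortal time would be counted; the problem would be selection.

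It is also fair to say that Fisher's conservatism absorbs small differences in loss.

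**Conclusion.** The concern holds as a gap with a conditional bias. The plan defines no efficacy population, and its wording points to treated patients. If untreated patients are left out, and more are lost before Day 1 in Arm B than in Arm A, the comparison favours radiotherapy. Both conditions are plausible, but neither is stated.

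The size cannot be read from the documents. In the scenarios with losses in Arm B only and all of them non-responders, 2 to 8 of 56 unreplaced or 5% to 15% replaced, the spurious difference is about 1 to 4 percentage points, against a design difference of 20. The Fisher type I error exceeds the nominal 20% only from about 4 of 56 unreplaced, or somewhat over 7% with replacement. Smaller or equal losses leave it below nominal. Inflation above 20% is therefore possible but not shown. The case for a change rests on protecting the randomised comparison at little cost.

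**What to change.** In 29.1 and 18.3, state that:

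- the primary BOR comparison includes all randomised patients in the arm assigned;
- a patient never treated or never assessed counts as a non-responder;
- randomised patients are not replaced in the analysis.

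State randomisation as the time origin for PFS and OS. Keep a treated-patient analysis as a sensitivity analysis. The 96-week response window can stay tied to Day 1, since imaging is scheduled by treatment day; the population is what needs to change.

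The cost is wording, plus the randomisation date and outcome status of patients who never start. Response rates become slightly lower. Power falls somewhat if patients never start: from 90% to about 86% if 5% of Arm B never start and 40% is the rate among treated patients.
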